10.3.2 Primary analysis

The primary outcomes (WEMWBS (ECoWeB-PROMOTE); PHQ-9 (ECoWeB-PREVENT) and secondary outcomes will be compared at 3-month follow-up. The primary and secondary continuous outcomes will be reported descriptively (mean and standard deviation (SD)) and inferential comparisons will be reported between the three treatment contrasts ((1) usual practice plus personalised digital self-help EC vs. usual practice alone; (2) usual practice plus non-personalised automated digital CBT self-help vs. usual practice alone; (3) usual practice plus personalised digital self-help EC vs. usual practice alone; (3) usual practice plus personalised digital self-help EC vs. usual practice plus non-personalised automated digital CBT self-help) using linear modelling. All analyses will be based on an intention to treat principle (i.e. according to original allocation irrespective of intervention adherence) and will include participants with complete outcome data at 3-month follow-up, and will adjust for baseline outcome score (where relevant) and minimisation variables (age, gender, country). Furthermore, we will adjust for any baseline participant characteristics that are substantively unbalanced at baseline (defined as a difference ≥ 10 percentage points across categories for a categorical variable, or a difference in means >1 SD for continuous variables), and if the characteristic is thought to be predictive of outcome. Binary secondary outcomes (occurrence of major depressive disorder; generalized anxiety disorder) will be reported as proportions and analysed used logistic regression.

10.3.3 Secondary analyses

A number of secondary analyses will be conducted.

1. 12-month follow-up comparison

Primary and secondary outcomes will be compared at 12-month follow-up using the statistical approach outlined above.

2. Repeated measures comparison including all timepoints

Primary and secondary outcome measures will be compared at all follow-up timepoints (1, 3, 12 months) using repeated measures analyses, including all participants with data available for at least one of the three follow-up timepoints.

3. Differential adherence analysis

Differential adherence within the active treatment arms is anticipated, which could impact the outcomes. Ideally, we wish to compare participants who adhere to their intervention with those in the comparator arm who would also have adhered to the treatment had they been allocated to it. To address this issue we will undertake a complier average causal effect (CACE) model, using a 2-stage least squares instrumental variable regression model. Such models will be performed for the continuous primary and secondary outcomes at 3- and 12-month follow-up using observed data only, and will include the covariates adjusted for in the linear regression models. The CACE analyses will be considered as secondary analyses. The definition of a 'complier' will be: (i) complete at least one Challenge (some psychoeducation) and at least four Challenges completed or ten Tools used (to capture practice) OR (ii) (to capture combined usage) at least ten Challenges or Tools completed (any combination), including at least one Challenge and one Tool. (The definition of a 'complier' may be subject to further revision.)

4. Imputation of missing data

Patterns of missing outcome data at follow-up will be extensively investigated. Multiple imputation models will be used to impute missing primary and secondary outcome data at all follow-up time points. Results for the between group comparisons based on these imputed data sets will be presented in addition to complete case regression analyses described above. Propensity for missingness associated with baseline characteristics will be investigated; imputation models will include treatment allocation as well as minimisation variables, baseline variables, and any variables associated with missingness or included in the models as covariates due to baseline imbalance. Such imputation models are based on the assumption that missing data is 'missing at random', which may not be a valid assumption in this context. Nevertheless, use of imputed data will increase power if there is substantive missing data, and is the least likely method to introduce bias. Imputation models will be informed by treatment arm, baseline scores, other covariates to be included in the model, and other baseline characteristics found to predict outcome or propensity for missingness (logistic regression models will be used to investigate the associations between baseline characteristics and missingness). Regression models using the imputed data will be considered as a secondary analysis.

10.4 Subgroup analyses

Primary and secondary analyses will be extended to explore potential subgroup effects by including interaction terms between the intervention allocation and the minimisation variables (age, gender, country).

To investigate differential treatment effects across subgroups of participants, we will perform a series of models, for the primary outcome only at 3-and 12-month follow-up, including an interaction term between treatment arm and the participant characteristic (as well as the other covariates to be adjusted for; each model will include one interaction term only). The participant characteristics to be investigated for differential treatment effects are age (continuous and dichotomised as for the minimisation algorithm), country and gender. The interaction terms will be reported as coefficients and 95% confidence intervals, with a global p-value. It is acknowledged that these analyses will have limited statistical power, and hence are exploratory in nature, and the results should be viewed with caution.

10.5 Interim analysis and criteria for the premature termination of the trial

No interim analyses are planned. In order to detect potential harms the study will monitor potential adverse effects. Adverse and serious adverse effects will be reported to TSC who will recommend discontinuation of the trial if there is cumulative evidence that the intervention may cause harm. There are no plans to terminate the trial prematurely due to futility.

10.6 Other statistical considerations.

Comparisons will be made between all three treatment allocations (personalised EC self-help vs. online CBT self-help; personalised EC self-help vs. usual practice; online CBT self-help vs. usual practice). No formal p-value adjustment will be made for multiple testing; the results of the ITT observed data analyses will be interpreted first, with the results of the additional analyses interpreted in this light. Interpretation of results will draw focus on confidence intervals rather than emphasising p-values.

Primary analyses will be performed by a statistician who remains blinded to group allocation, and will be presented as such to the investigators. The results will be discussed and interpreted prior to the unblinding of group allocations. Additional analyses will then be performed following unmasking.

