7.3 The randomisation scheme

Random selection to the 3 arms (offering EC self-help app; offering CBT self-help app; or continuing with self-monitoring app alone – usual practice) will be conducted automatically by means of a secure web service created and managed by the Exeter Clinical Trials Unit (CTU) in conjunction with the trial statistician. This will be independent of the trial researchers. To promote balance across key participant characteristics across groups, we will minimize allocation by sex, country from which participant is entering the trial (reflecting trial site; i.e., UK; Spain, Germany, Belgium), and age (16-17 vs. 18-22 years). We split the sample into two age ranges to reflect naturally occurring transitions (e.g., between secondary education vs. tertiary education; into the workforce) and that the concerns and issues of 16/17 year olds may differ from those of 18 to 22-year olds. To maintain concealment, the minimisation algorithm will retain a stochastic element and the first 50 participants will be allocated to each by simple random allocation.

Protection from bias

We will adopt prior registration and publication of the trial protocol. Independent web-based computerised randomisation will be conducted to ensure generation of an unpredictable allocation sequence and concealment of participant allocation and of allocation sequence and prevent selection bias and confounding. We will use standardised assessments with data collected automatically through the website. The use of self-administered measures will eliminate observer bias. A detailed statistical analyses plan will be prepared and agreed with Trial Steering Committee before any analysis is

conducted. The trial statistician will remain blinded to group allocation until the main data analyses have been undertaken and interpretation of the trial results have been agreed by the relevant committees. Attrition bias will be minimised by having robust trial procedures to prevent data loss such as email, text and phone reminders to encourage follow ups.

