10.3 Statistical analysis plan

A detailed statistical analysis plan (SAP) is to be produced; the main points of the statistical analysis are summarised here – for full details see project SAP whose details supercede this. The statistical analysis for each trial will follow the same broad guidelines; any adaptations for each trial individually we reported

in the detailed SAP. The SAP will be approved by the TSC prior to end of participant recruitment. Any amendments to the TSC will be documented and approved by the TSC on an ongoing basis.

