#### 7. General analysis considerations

#### 7.1 Timing of analyses

The first set of statistical analyses will be performed when the 3-month outcome data is available and the database has been locked. At this point, the statistician will perform the 3-month inferential analyses (as well as descriptive analyses for 1- and 3-month data), whilst being unaware of treatment arm allocation. These analyses will be performed on the ITT population using observed data only. Following presentation of the results with anonymised allocations, the allocations will be revealed for interpretation of the results. Following revelation of treatment allocations, the remaining analyses of 3-month outcome data will be performed. Following completion of 12-month data collection and database lock, the remaining analyses of the 12-month outcome data will be performed. At this point the repeated measures analyses and analyses including imputed and observed data will be performed.

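### The SAP reveals allocations so that the 3-month results can be interpreted, whereas the Protocol requires interpretation to be agreed first; a few open analysis choices are not tied to the masked period

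*Protocol*

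**What the plan says.** Protocol 10.6 has a blinded statistician run the primary analyses and present them masked. It continues: "The results will be discussed and interpreted prior to the unblinding of group allocations". Further analyses come afterwards: "Additional analyses will then be performed following unmasking". Protocol 7.3, under protection from bias, keeps the trial statistician blinded "until the main data analyses have been undertaken and interpretation of the trial results have been agreed by the relevant committees".

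Protocol 7.4 is looser. It keeps the statisticians and the Steering Committee blinded until the analysis is complete and interpretation is under way, which is compatible with unblinding at the interpretation stage.

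SAP 7.1 has the 3-month inferential analyses run masked, by intention to treat on observed data, and shown with anonymised arms. Then "the allocations will be revealed for interpretation of the results". After that, "Following revelation of treatment allocations, the remaining analyses of 3-month outcome data will be performed".

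On precedence, Protocol 10.3 introduces its summary of the analysis with "for full details see project SAP whose details supercede this".

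On the complier average causal effect (CACE) analysis, Protocol 10.3.3 and SAP 6.6 define a complier and add: "The definition of a 'complier' may be subject to further revision". No deadline is given.

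**The concern.** Interpretation in this trial needs judgement. Each trial has three contrasts with no multiplicity adjustment, and Protocol 10.6 puts the weight on confidence intervals rather than p-values. The primary result will be read beside several alternatives: COVID-19 adjustment, the app-outage analyses, out-of-window data, possibly exclusion of repeat applicants, and later imputed data and the CACE analysis. Partners in the consortium that runs the trial wrote the app content, and the stated hypotheses favour the personalised emotional competence (EC) arm.

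Agreeing the reading before anyone knows which arm is EC is the safeguard that the Protocol offers against a reading that leans towards the expected answer. The SAP order drops it without giving a reason. Any choice still open once allocations are known carries the same exposure.

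**Working it through.** **Order of events.** No planned figure is at issue, so the first check sets the texts side by side.

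| Step | Protocol 10.6 and 7.3 | SAP 7.1 |
|---|---|---|
| 1 | Primary analysis, masked | 3-month analysis, masked |
| 2 | Presented masked | Presented masked |
| 3 | Interpreted (7.3: agreed by committees) | Allocations revealed |
| 4 | Allocations revealed | Interpreted |
| 5 | Additional analyses | Remaining 3-month analyses |

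Steps 3 and 4 are reversed. Steps 1, 2 and 5 agree, so running further analyses after unmasking is common to both documents and is not a conflict.

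**Which choices are open.**

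- Out-of-window data: SAP 3.8 commits to this sensitivity analysis, although SAP 6.3 speaks only of a possibility. Timing relative to unmasking is not stated.
- COVID-19 covariate (SAP 6.7) and the two 3-month outage analyses (SAP 6.9): specified in advance. They use observed data and can be read as part of the masked set.
- Imputed-data analyses: SAP 7.1 places them after the 12-month lock.
- Repeat applicants (SAP 6.8): optional, depending on how many there are. Timing not stated.
- Complier definition: open to revision, no deadline.
- 12-month and repeated-measures outage sensitivity analyses (SAP 6.9): whether to run them is decided after the 3-month results. SAP 3.9 has the statistician aware of allocations for the 12-month database.

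The last three items are the real discretion, and the last is the clearest case of a choice that depends on results.

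**Illustration of selective emphasis.** Take one contrast under the null.

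- Revised target 3599, of whom 1457 disrupted (SAP 6.9). Undisrupted: 3599 − 1457 = 2142, and 2142/3599 = 59.5%.
- Z(full) = √0.595 × Z(undisrupted) + √0.405 × Z(disrupted), so the correlation of the full and undisrupted results is √0.595 = 0.771.
- One result only: P(Z > 1.96) = 2.5%.
- Either result may be stressed: P(either Z > 1.96) = 0.0399, or 4.0%.
- Add an imputed result whose correlation with the full-sample result is assumed, not taken from the documents: 0.95 gives 0.0459 (4.6%) and 0.90 gives 0.0486 (4.9%).

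This assumes the same disrupted share and the same retention and variance in every arm. The imputed result is linked to the undisrupted one only through the full sample.

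**The case against.** The strongest reply has four parts.

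First, the Protocol does not speak with one voice: 7.4 already fits the SAP order. Precedence is also narrower than it looks. Protocol 10.3 concerns the summary in section 10 and does not plainly override 7.3, and SAP 1.4 says the two documents are to be used together. This stands, and is itself a reason to reconcile the sections.

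Second, a reader might infer that every discretionary sensitivity analysis waits until after unmasking. The documents do not support that. Most of the 3-month analyses are pre-specified, and several fit SAP 7.1's description of the masked set. For out-of-window data and repeat applicants, later timing is only an inference from the words remaining and additional.

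Third, there are safeguards. Both documents fix a reading order with the primary results first. The CACE and imputed analyses are labelled secondary, and the outage analyses post hoc and exploratory. SAP 1.7 treats revisions made after unblinded interpretation as post hoc and asks for strong justification, which would catch a late change to the complier definition. It would not catch choices that the SAP already permits, namely repeat applicants and the 12-month and repeated-measures outage analyses.

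Fourth, a reader might take 4.0% to 4.9% as the trial's type I error. It is not: the calculation treats a sensitivity result as interchangeable with the primary one, which the reading order does not allow.

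**Conclusion.** The contradiction between Protocol 10.6 and 7.3 on one side and SAP 7.1 on the other is plain in the text. It reverses a protection against bias that the Protocol sets out. It should be corrected, but it does not threaten the primary estimate, which is produced and first shown masked under either document.

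What is exposed is the interpretation of three contrasts and the open choices: repeat-applicant exclusion, the complier definition, and the 12-month and repeated-measures outage sensitivity analyses. The size of any effect on conclusions cannot be derived from the documents. The rise from 2.5% to between 4.0% and 4.9% shows only what unrestricted emphasis could do for one contrast, and its upper part rests on the assumed correlation of 0.90 to 0.95.

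**What to change.** 1. Amend SAP 7.1, and align Protocol 7.3, 7.4 and 10.6 with it, so that the primary results are presented as arms A, B and C and a written interpretation is agreed before allocations are revealed.
2. While still masked, fix the complier definition and delete the sentence allowing further revision from Protocol 10.3.3 and SAP 6.6.
3. While still masked, decide whether the repeat-applicant analysis and the 12-month and repeated-measures outage sensitivity analyses will be run. The SAP's wish to let the 3-month findings inform the outage decision can be kept, because those findings would be available under masked codes.
4. State in SAP 7.1 that the pre-specified 3-month observed-data sensitivity analyses (out-of-window, COVID-19, outage) belong to the masked set, and bring SAP 6.3 into line with 3.8 on out-of-window data. The written interpretation can then record how they bear on the primary result. Without such a record, emphasis among them could still be chosen later.

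Imputed-data analyses may stay after the 12-month lock, as SAP 7.1 plans. The cost is wording in the two documents and one masked results meeting, with some 3-month sensitivity analyses possibly run earlier. No extra data or participants are needed.

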10.7 Mediational analyses

Quantitative mediational analyses will be described in the process evaluation analysis plan.

Mediational analyses will test the hypotheses that the personalised EC intervention is effective by changing unhelpful habits and improving EC skills. Each of these potential mediators of the primary outcome is a continuous variable, assessed via the EC instruments at 1-, 3- and 12-month follow-up, potentially examined as latent variables/factors from a factor analysis.. Analyses will include the use of instrumental variables to account for effects of unobserved confounding on mediators (Dunn et al., 2005).

10.8 Economic evaluation

Economic analysis

The economic analysis will take a societal perspective and undertake a cost-consequence approach. Because all the resources used, costs, and outcomes are transparently listed in the cost-consequence analysis, decision makers can select the information that is of most interest to them. Furthermore, the choice of cost-consequence analysis supports current approaches used by healthcare decision-makers to value the efficiency of healthcare interventions across Europe (Angelis et al., 2017).

Unit costs of health and social care will be taken from appropriate national publications to reflect differences in costs between countries (for example, Curtis & Burns, 2018). Productivity losses will be valued using the human capital approach (Koopmanschap & Rutten, 1996). Wage rates for each country will be derived from European sources such as Eurostat. Responses to the EQ-5D-3L will be converted to utility values using the EuroQoL general population tariff values for each country.

Within country analyses of the differences between the trial arms will be undertaken. Although the distribution of costs is commonly skewed in populations of this kind, analyses will compare mean costs between groups using standard parametric regression models adjusted for minimisation variables and baseline costs. The robustness of the parametric tests will be confirmed using bias-corrected, non-parametric bootstrapping (Efron & Tibshirani, 1993; Barber & Thompson, 2000). As with primary and secondary outcomes, between group differences in costs and EQ-5D-3L will be presented as means and 95% CIs using STATA v14.2.

Given the differences in cost structures (health and social care, and wage rates) and differences in the population tariffs between countries no formal analyses of differences between costs and utility values between countries will be undertaken. However, the differences between the number and type of resource use and days away from work and employment will be examined.

10.9 Implementation Science

As part of the research there will be qualitative investigation of participant experiences using the App. A random sub-sample of participants will be contacted by our collaborating research team at the University of Oxford (ECoWeB WP8) to see if they would be willing to take part in an additional interview 3 and or 12 months after being randomised into the trial. All participants are asked if they would be willing to be contacted about future/additional research in consent form B. The ECoWeB WP8 information sheet and consent form C have been uploaded for review with this protocol.

11 DATA MANAGEMENT

11.1 Data collection tools and source document identification

Database management, data curation and sharing will be supported by UNEXE and EXCTU. Efficacy/effectiveness parameters will be directly and automatically entered into an SQL database programmed by Exeter CTU. At assessment participants will directly complete electronic questionnaires and tasks online using the Qualtrics website and this data will be automatically processed to extract relevant anonymised parameters (from which an individual's identity cannot be detected) and will be stored in the secure database prepared and managed by EXCTU. The App data collected from participants will be collected from MSS through an https website

An eCRF will be designed and set up for participants to enter data electronically by completing the website assessments designed to capture relevant pseudo-anonymised and de-identified data. Programmed and manual queries on the data completed in the eCRF will be raised centrally by UNEXE. This monitoring process of the clinical database will be done in real time throughout the course of the trial. After the database has been locked, cleaned and findings dissemination and following successful evaluation by the ECoWeB Steering Committee, access to the project data may be granted to other parties, following rules that will be defined in a specific agreement between the partners and third parties. Only data required for the trial will be collected.

11.2 Data handling and record keeping

A separate data management plan accompanies this trial protocol.

11.3 Access to Data

Direct access will be granted to authorised representatives from the Sponsor, host institution and the regulatory authorities to permit trial-related monitoring, audits and inspections- in line with participant consent.

